8 STUDY DESCRIPTION

8.1 Study Design

- Phase II, open-label, single-center dose-ranging study.

- Three treatment cohorts of 13 subjects each are planned, potentially for each of the routes of administration (intravenously and subcutaneously). The different cohorts are composed of subjects taking three of the four commercially-prescribed levels of daily oral dosing: 10, 20, and 40 80 mg. Subjects are treated with daily doses of injectable atorvastatin intended to be non-inferior to the efficacy of their stable oral dose during the Lead-in Period.
- Enrollment of subjects into any one of the cohorts that does not prove to meet the primary endpoint, or otherwise shows a lack of efficacy, is terminated as soon as this determination is made, and a new cohort intended for 13 subjects is opened at an adjusted dose with intentions to meet the primary endpoint. See [Section 9.3.6.2.2](#).
- Subjects remain on the replacement treatment with atorvastatin for injection for 15 days, followed by a one-week follow-up period.
- Assessments include the following:
 - Pharmacokinetic (PK) profile evaluation of both the oral and IV dosing and, starting with Amendment 3, the SC dosing regimen.
 - Cholesterol (LDL-C) levels to assess efficacy
 - Safety assessment, including markers of rhabdomyolysis
- **Sub-study (Amendments 1 and 2 only):** If remaining on oral atorvastatin in the follow-up period, subjects that individually meet the study objective (Day 15 LDL-C \leq 125% of baseline level) may substitute a daily oral dose of atorvastatin for a subcutaneous dose of the same volume as the intravenous dose to which they were assigned. Plasma levels of atorvastatin and the two metabolites are measured for a 24-hour period to assess the pharmacokinetic parameters of the subcutaneous route.
- Schedules of assessments are summarized in [Table 9-1A](#) and [Table 9-1B](#) depending on the medication history of the subject when they entered the study.

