8.3.3 Drug Accountability Procedures

Atorvastatin injection, labeled for investigational use, will be provided by Cumberland Pharmaceuticals Inc. The investigator is required to keep complete and accurate records of the receipt, dispensation, disposal and return of all clinical trial drugs provided during the conduct of the study.

For subjects entering the study already taking oral atorvastatin, the product will continue to be obtained according to the subjects' standard methods through the lead-in and follow-up periods. Accountability is not formally documented in these cases; however, in determining each subject's eligibility, the Investigator assures to the best of his or her knowledge that the subject has been on a stable dose of oral atorvastatin.

Subjects that were not taking oral atorvastatin when entering the study are provided it by the study at the assigned dose. Drug accountability for these subjects is calculated during the five-week lead-in period so that compliance for that patient is understood and eligibility can be confirmed.

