9 STUDY PROCEDURES

9.1 Study Overview

A schematic of the overview of the study is shown below in [Figure 9-1](#). Three types of patient populations, categorized by statin use prior to study participation, are all potentially eligible for the study as shown below, and their progression through the screening and lead-in periods follows the pathway determined by their pre-study use of statins:

- Patients taking oral atorvastatin prior to the study
- Patients taking statins other than atorvastatin prior to the study
- Patients not taking any statins prior to the study.

The study consists of a screening visit that determines a subject's eligibility to enter a lead-in phase where they will start or continue taking daily oral atorvastatin. Specific eligibility requirements are dependent on their pre-study statin use.

During the Lead-in Period, daily dosing of oral atorvastatin allows the determination of baseline LDL-C levels and also provides PK data from steady-state oral administration that will be compared to that from the intravenous administration.

The treatment period consists of an open-label treatment of 15 daily intravenous or subcutaneous doses of atorvastatin injection. A 7-day follow up period follows and concludes with a phone call from the Investigator or designee to the subject to collect information on any possible adverse events or changes in concomitant treatments.

Subjects eligible for the Sub-study and willing to participate receive a subcutaneous injection of atorvastatin on Day 22 and complete PK sampling the following day. The follow-up phone call, as noted above, is completed on Day 29.

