9.3.4.1 Pharmacokinetics for Oral Dosing

Samples will be drawn from all participating subjects at the Lead-in End Visit in order to define the steady-state pharmacokinetic profile of the respective, stable dosing regimen on oral atorvastatin.

The subject is directed to refrain from taking their daily oral dose of atorvastatin at home, but then to bring the dose to the clinic for the PK visit. The visit is scheduled such that the dose is taken in the clinic at a time of day as close as possible to the time that the subject typically takes their oral dose.

At the oral PK visit, samples are drawn and processed per the procedure detailed above in [Section 9.3.4](#) at the following times; allowable windows are listed in [Table 9-3](#):

- Within 60 minutes prior to taking the oral dose of atorvastatin.
- At the following times after taking the oral dose:
 - 30 minutes
 - 1 hour
 - 2 hours
 - 4 hours
 - 6 hours
 - 8 hours

Levels of atorvastatin and metabolites measured from the pre-dose timepoint are imputed as the Hour 24 levels since the subject is on daily, constant dosing.

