9.3.4.3 Pharmacokinetics for Subcutaneous Dosing (Sub-Study)

Subjects must first meet the eligibility criteria listed in [Section 8.4.4](#) before participating in the subcutaneous PK sub-study. The Investigator ensures the subject has given and documented their consent to participate in the sub-study before performing related procedures.

As a result of the review of real-time, open-label LDL-C values, the sponsor informs the Investigator as to which subject(s) qualify for the sub-study. This determination is made following the subject's Day 15 visit and the subsequent reporting of the LDL-C level from the visit. The Investigator inquires of the subject's ability and continued consent to participate in the sub-study (Inclusion Criteria).

Eligible subjects that have consented to the sub-study will have resumed taking daily oral atorvastatin at their lead-in dose since Day 16. They then return to the study center on Day 22 \pm 2 days after being instructed by the Investigator to refrain from taking their daily oral dose of atorvastatin at home on the day of the visit.

Subjects receive a subcutaneous dose of atorvastatin injection ([Section 8.3.2.2](#)), then samples are drawn at the following times after the time of the SC dose; allowable windows are listed in [Table 9-3](#):

- 30 minutes
- 1 hour

- 2 hours
- 4 hours
- 6 hours
- 8 hours
- 24 hours

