9.3.6.2.1 Initial Cohort (10 mg PO Atorvastatin)

Subjects belonging to the 10-mg *per os* (PO) baseline cohort group (those that were taking 10 mg oral atorvastatin per day during Lead-in) are the first to be enrolled on the study. As shown below in Table 9-4, the initial subject in the 10 mg cohort is assigned to 2 mg IV atorvastatin injection as their daily dose. Subsequent subjects from the 10 mg PO Lead-in group are enrolled and treated with 2 mg IV daily while LDL-C values from their Day 8 and Day 15 study visits are reported and compared to baseline values in real time.

Table 9-4 **Intravenous Dosing by Lead-in Cohort**

Lead-in Daily Dose of Oral Atorvastatin	Initial Targeted, Daily Intravenous Dose	Maximum Daily Intravenous Dose, after escalations
10 mg	2 mg	5 mg
20 mg	4 mg	10 mg
40 mg	8 mg*	20 mg

* Targeted starting doses for the cohort are shown; however actual starting doses may be adjusted pending findings from earlier cohorts.

LDL-C values are monitored by the sponsor in real time and, if consistent and significant trends are seen to suggest that a cohort is not receiving an adequate dose, a dose adjustment for the cohort is warranted. Ongoing subjects in the treatment period of the affected cohort at the time of the decision to adjust the dose are contacted by the Investigator and directed to immediately discontinue the intravenous dosing and withdraw from the treatment period. The subjects are then not eligible for the sub-study.

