9.3.6.3 Subcutaneous Dosing (Sub-Study)

Those subjects that are participating in the sub-study resume their Lead-in daily oral dose of atorvastatin beginning on Day 16. Their oral dose is withheld on the day of their Day 22 Visit while they return to the clinic for a subcutaneous injection given as close as possible to the time of day at which they take their oral dose. The dose amount administered is the same as that which was taken intravenously during the treatment period.

Subjects that are not participating in the sub-study resume their standard of care treatment, if any, for hypercholesterolemia while they await their Day 22 follow-up call.

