Prior to administration, blood samples are drawn for analysis of hematology and serum biochemical levels, including a lipid profile. Labs are drawn and processed according to standard local processes and analyzed at the Investigator's local clinical laboratory. Analytes to be measured are listed in [Table 9-2a](#). The Investigator reviews reported values in comparison to those reported at the screening and treatment visits and any changes that are deemed undesirable and clinically significant are reported as adverse events. Subjects with clinically-significant changes in lab values are monitored at unscheduled visits until values return to normal or until a cause other than the study drug is determined.

LDL-C and HDL-C levels are transmitted to the sponsor as soon as available.

Samples for Pharmacokinetic profiling of intravenous atorvastatin are taken per [Section 9.3.4.2](#).

A urine pregnancy test is administered for all women of child-bearing potential.

Subjects that entered the study taking oral atorvastatin are directed to resume taking their oral atorvastatin on the day following the Day 15 (or withdrawal) visit at the same dose level as that taken during the Lead-in Period.

Subjects that did not enter the study taking oral atorvastatin but continue to participate in the Sub-study are dispensed oral atorvastatin at the same dose as that taken during the Lead-in Period. Patients that are in the Sub-study are directed to refrain from taking their oral dose at home on the day of their Day 22 Visit.

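### The oral hold in the SC sub-study ends before the 24-hour sample, and SAP 5.7.2 has no rule for a tablet taken ahead of that draw

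*Protocol*

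**What the plan says.** The oral hold is stated several times, always for the injection day only. Protocol 9.3.4.3 has subjects return after "being instructed by the Investigator to refrain from taking their daily oral dose of atorvastatin at home on the day of the visit". Protocol 9.4.4.6 (Day 15) says "Patients that are in the Sub-study are directed to refrain from taking their oral dose at home on the day of their Day 22 Visit". Protocol 9.3.6.3 and the footnotes to the schedules (Protocol Tables 9-1A and 9-1B, SAP Tables 3A and 3B) have the same scope.

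On timing, Protocol 9.3.6.3 calls for "a subcutaneous injection given as close as possible to the time of day at which they take their oral dose". Protocol 9.1 says subjects "receive a subcutaneous injection of atorvastatin on Day 22 and complete PK sampling the following day". Protocol Table 9-3 and SAP 4.1.2 allow 60 minutes either side of Hour 24.

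On continued oral dosing, Protocol 8.1 opens the sub-study description with "If remaining on oral atorvastatin in the follow-up period". Protocol 8.3.3 has subjects who entered on oral atorvastatin obtain it by their "standard methods through the lead-in and follow-up periods". Subjects who did not enter on it are dispensed it for the sub-study (Protocol 9.4.4.6), and the text does not say whether they take a tablet on the day after the injection.

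On analysis, SAP 5.7.2 gives a specific rule for the single-dose SC pre-dose value and none for the 24-hour value. Protocol 12.3 excludes the sub-study from the Hour 24 imputation, so that value is a real sample.

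**The concern.** The injection replaces one tablet at the usual hour, so the next tablet falls due at about Hour 24. A subject who takes it at home and then travels to the clinic has followed every instruction, yet the sample contains freshly absorbed oral drug. The oral profile is better protected: Protocol 9.3.4.1 tells subjects not to dose at home on the Lead-in End day and to bring the tablet to the clinic.

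No SC sample lies between 8 and 24 hours, so the last one carries the tail of AUC0-24 and anchors the terminal slope. Oral drug in it makes SC exposure look larger and longer-lasting. Exploring SC pharmacokinetics is a stated objective, and the Amendment 1 and 2 data are still covered by the SAP although the sub-study is closed.

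**Working it through.** The plan states no figure on this point to reproduce. The check has a timing part and an illustrative size part.

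**Timing.** Let the usual tablet hour be T.
- Injection at T on Day 22; draw between T + 23 h and T + 25 h; next tablet due at T + 24 h.
- In the central case tablet and draw coincide.
- With an injection at T and a tablet at its usual hour, the tablet precedes the draw by at most 1 h. A later injection widens that gap.
- A tablet at or after the draw adds nothing.

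**Weight of the 24-hour value.** By the linear trapezoid it is (24 − 8)/2 = 8 h. Each unit of oral-derived concentration adds 8 unit·h to AUC0-24.

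**Effect of a given contamination.** Assumed profile: C(t) = exp(−kt), k = ln 2 / half-life, sampled at 0, 0.5, 1, 2, 4, 6, 8 and 24 h. Contaminated C24 = exp(−24k) + f × C8, where f is the oral contribution as a share of the 8-hour level. The terminal slope is fitted to 6, 8 and 24 h.

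Worked case, half-life 7 h and f = 0.25:
- C8 = 0.4529 and true C24 = 0.0929.
- Contaminated C24 = 0.0929 + 0.25 × 0.4529 = 0.2061.
- AUC0-24 goes from 9.904 to 9.904 + 8 × 0.1132 = 10.810, up 9.1%.
- Fitted half-life is 13.2 h with adjusted R-squared 0.984.

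| f | Linear AUC0-24 rise (true half-life 4 / 7 / 10 / 14 h) | Fitted half-life, h | Extrapolated share of AUCinf |
|---|---|---|---|
| 0.10 | 3.1 / 3.7 / 3.7 / 3.7% | 5.9 / 9.1 / 12.9 / 18.3 | 5 / 15 / 26 / 40% |
| 0.25 | 7.7 / 9.1 / 9.4 / 9.3% | 8.7 / 13.2 / 19.0 / 29.0 | 12 / 27 / 41 / 56% |
| 0.50 | 15.4 / 18.3 / 18.7 / 18.7% | 15.3 / 25.6 / 44.4 / 111.8 | 29 / 50 / 68 / 86% |

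The SAP does not name the trapezoid rule. With log-down the AUC0-24 rises are 5-9%, 12-18% and 22-30%.

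**What the SAP 5.7.2 rules catch.**
- Adjusted R-squared is 0.97 or above in every case at f = 0.10 and 0.25, so the half-life would be reported. It falls below 0.8 only at f = 0.50 with half-lives of 10 and 14 h.
- The 20% extrapolation rule withholds AUCinf in all but three contaminated cases: 4 h and 7 h at f = 0.10, and 4 h at f = 0.25. In the last of these AUCinf is up 21%.
- Neither rule touches AUC0-24.

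**How large f could be.** The oral dose is 5 times the injected dose at the starting doses: "the initial subject in the 10 mg cohort is assigned to 2 mg IV atorvastatin injection as their daily dose" (Protocol 9.3.6.2.1), with 20/4 and 40/8 mg in Table 9-4. It is at least 2 times at the 50% cap in Protocol 9.3.6.2.2. Let M be the systemic oral amount relative to the SC dose, assumed 0.25 to 1. That means a relative bioavailability of 5-20% at the 5:1 ratio or 12.5-50% at 2:1. For a tablet τ before the draw, with absorption lag L and x = max(τ − L, 0):

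f = M × ka/(ka − k) × [exp(−kx) − exp(−ka·x)] / exp(−8k)

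With half-life 7 h and ka = 1 per h:

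| Tablet before draw | No lag | 15-min lag | 30-min lag |
|---|---|---|---|
| 5 min | 4-18% | 0 | 0 |
| 15 min | 12-48% | 0 | 0 |
| 30 min | 21-85% | 12-48% | 0 |
| 60 min | 33-132% | 28-112% | 21-85% |

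With no lag, varying the half-life over 4-14 h and ka over 0.5-2 per h widens the 15-minute row to 4-154%. The documents fix none of these inputs.

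**The case against.** The design points to a trough sample: one tablet is replaced at its usual hour, and the next is due when the subject is expected at the clinic. With tablet and draw coinciding in the central case, contamination needs a tablet taken ahead of the draw. That stands. A reader might infer that the sub-study's 24-hour values are contaminated or its SC results biased. The documents do not support this, because they contain no dose times and no concentrations.

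General provisions could also be used. The PK Population requires data sufficient for reliable estimates (SAP 5.1), protocol deviations are identified before lock from an open list (SAP 5.2), and analysis changes can be documented (SAP 5.12). These permit case-by-case handling but set no rule. The bar on major protocol deviations would not naturally reach a tablet that no instruction forbids.

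A remedy may recover little, since accountability is not formally documented for subjects on their own supply (Protocol 8.3.3). That also stands. So does the comparison of scale: on this schedule the linear rule alone overstates true AUC0-24 by 3% (half-life 14 h) to 14% (4 h), against 3-4% from contamination of 10% of C8.

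**Conclusion.** The gap is real but minor. A subject can follow the plan exactly and still supply a 24-hour value containing fresh oral drug, which no specific rule would remove from AUC0-24 or the terminal slope. The point is firm for subjects who entered on oral atorvastatin and open for those dispensed it for the sub-study.

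The illustrated rise in linear AUC0-24 is about 3-19% for an oral contribution of 10-50% of C8. A true 7 h half-life could be reported as 13.2 h at 25%. These sizes rest on assumed half-life, absorption rate, relative bioavailability and lag, and the frequency is unknown. The single-dose SC results are descriptive, lie outside the Bioavailability Population and feed no efficacy decision. Cohort 4 supplies multiple-dose SC data separately.

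**What to change.** Add one paragraph to SAP 5.7.2 for the single-dose SC data, fixed before analysis:

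1. Establish from source records or site query the time of any oral atorvastatin dose between the SC injection and the 24-hour draw.
2. Where a dose before the draw is confirmed, set the 24-hour value to missing for AUC0-24, Kel, T1/2, AUCinf, CL/F and volume, with no minimum interval. A tolerance such as 15 minutes is not advisable: with no lag, a tablet 15 minutes before the draw could add 12-48% of C8. The Lead-in oral profile ("Samples will be drawn from all participating subjects at the Lead-in End Visit", Protocol 9.3.4.1) has no post-dose sample before 30 minutes, so it cannot validate a shorter threshold.
3. Where the time is unknown, keep and flag the value, and give a sensitivity summary without flagged values.
4. Report Cmax and AUC0-8 for all sub-study subjects, noting that both still include residual drug from earlier tablets. An assumed residual of 5-20% of SC Cmax would make up 3-17% of AUC0-8.

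The cost is one paragraph, one query per sub-study subject and one extra table. Subjects with a confirmed early dose lose AUC0-24 and usually AUCinf and CL/F, because extrapolation from 8 h is 25-67% for half-lives of 4 to 14 h, above the 20% limit. Some dose times will not be recoverable. No protocol change is needed, since the sub-study is closed under Amendment 3.

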9.3.5 Pharmacodynamic Assessments

The main efficacy objectives of the study are assessed through the lipid profile measured at Lead-in End Visit, Day 8 and Day 15. (See [Tables 9-1A](#) and [9-1B](#)).

9.3.6 Dose Assignments

Subjects are assigned to one of three lead-in cohorts based on their daily dose of oral statin on which they entered the study, if applicable, and their screening value for LDL-C. Lead-in cohorts are categorized by the amount of daily, oral atorvastatin the corresponding subject will take (10, 20, or 40 mg). Following the completion of the Lead-in Period, subjects are assigned a daily intravenous or subcutaneous (Amendment 3) dose on which they remain during their complete treatment period, including the sub-study, if they participate. The dose for each cohort is determined by the sponsor and may be adjusted while the study is ongoing based on the continual monitoring and evaluation of safety and efficacy parameters.

9.3.6.1 Lead-in Period Dosing

Subjects that pass screening and enter the Lead-in Period are assigned an oral dose by the sponsor. Subjects enter one of the three possible Lead-in cohorts: 10, 20, and 40 mg. The sponsor will communicate the dosing assignment for each individual subject to the Investigator in writing.

9.3.6.2 Intravenous Dosing

The goal of the intravenous dosing and any associated dose adjustments is to fill all three cohorts and meet the primary study endpoint for each while utilizing the lowest possible daily dose of intravenous atorvastatin injection.

Primary study endpoint (See [Section 7](#)): Eleven or more subjects in a dosing cohort of thirteen with a Day 15 LDL-C not more than 125% of their baseline LDL-C.

9.3.6.2.1 Initial Cohort (10 mg PO Atorvastatin)

Subjects belonging to the 10-mg *per os* (PO) baseline cohort group (those that were taking 10 mg oral atorvastatin per day during Lead-in) are the first to be enrolled on the study. As shown below in Table 9-4, the initial subject in the 10 mg cohort is assigned to 2 mg IV atorvastatin injection as their daily dose. Subsequent subjects from the 10 mg PO Lead-in group are enrolled and treated with 2 mg IV daily while LDL-C values from their Day 8 and Day 15 study visits are reported and compared to baseline values in real time.

Table 9-4 **Intravenous Dosing by Lead-in Cohort**

Lead-in Daily Dose of Oral Atorvastatin	Initial Targeted, Daily Intravenous Dose	Maximum Daily Intravenous Dose, after escalations
10 mg	2 mg	5 mg
20 mg	4 mg	10 mg
40 mg	8 mg*	20 mg

* Targeted starting doses for the cohort are shown; however actual starting doses may be adjusted pending findings from earlier cohorts.

LDL-C values are monitored by the sponsor in real time and, if consistent and significant trends are seen to suggest that a cohort is not receiving an adequate dose, a dose adjustment for the cohort is warranted. Ongoing subjects in the treatment period of the affected cohort at the time of the decision to adjust the dose are contacted by the Investigator and directed to immediately discontinue the intravenous dosing and withdraw from the treatment period. The subjects are then not eligible for the sub-study.

9.3.6.2.2 Dose Adjustments

Following are two criteria that may initiate a dose adjustment:

- Three or more subjects have a Day 8 and/or a Day 15 LDL-C \geq 125% of their baseline LDL-C. The dose is then increased for subsequent subjects.
- Three or more subjects have a Day 8 and/or Day 15 LDL-C \leq 75% of their baseline LDL-C AND the mean of the lowest available post-treatment values is \leq 85% of the mean of the baselines

In all scenarios, additional enrollment into the cohort is immediately stopped if the dose for the cohort is adjusted following an open-label review by the sponsor's clinical and medical teams. Enrollment into that cohort is then re-started at a new dose with the intention to enroll thirteen subjects. Doses will be adjusted by an amount not to exceed 25% of the preceding dose for that cohort.

The final dose will not exceed the maximum for that group as listed in [Table 9-4](#). The maximum intravenous or subcutaneous dose to be administered to any cohort level will not exceed 50% of the oral dose for that same cohort. Prior to increasing a dose, the sponsor's medical monitor reviews a listing of serum biochemical values from all subjects in the current cohort and determines if there are any concerns of safety issues. Subsequent investigational treatment can proceed at the increased dose once any safety concerns have been eliminated.

In the opposite scenario, where three or more subjects report an $LDL-C \leq 75\%$ of their baseline $LDL-C$ and the mean of the lowest available post-treatment values is $\leq 85\%$ of the mean of the baselines, the dose will be decreased following review of all treated subjects from that baseline group.

If subsequent dose adjustments are needed, the guidelines above continue to be followed.

Once a full cohort of 13 subjects have been enrolled and treated and the primary study objective has been met, the current dose is considered the established dose for that cohort and the next cohort initiates enrollment.

